5. STUDY TREATMENTS

5.1. Identity of investigational medicinal products

IMP will be provided by the pharmaceutical company Mylan A/S who will send the IMP and corresponding placebo to Kragerø Tabletproduksjon AS (see attachment), who will be responsible for packing and labelling of boxes according to the randomisation list. Kragerø Tabletproduksjon AS will deliver IMP to a designated pharmacy in each country which in turn will distribute IMP to

participating sites. The IMP will be handed out consecutively to participants for six months use (four boxes with 90 tablets each), in accordance with the randomisation list.

Kragerø Tablettproduksjon AS will create 200 sets of boxes containing methenamine hippurate and 200 sets of boxes containing placebo (lactose). The boxes will have identical labelling (see attachment). Only patient ID on the label will be linked to the randomisation list, telling which medication the patient has received.

Boxes with active substance consist of tablets with the active substance methenamine hippurate 1 gram. This is equivalent to the standard recommended dose of methenamine hippurate as presented in Summary of Product Characteristics (SmPC) (attachment). Boxes with placebo drug will contain the equivalent dose of lactose.

5.1.1. Doses and length of treatment.

Participants will be instructed to take one study tablet morning and evening for 180 days. This corresponds to a daily dose of 2 g methenamine hippurate or placebo daily. The dosage is according to SPC for preventive treatment. The length of treatment is line with previous studies which have used 6-12 months as length of treatment (13-16, 24-25). This is also in line with clinical practice, and we have chosen 6 months to maximise compliance in this vulnerable patient group.

5.1.2. Labelling

The acquisition, labelling, Qualified Person release and delivery of the methenamine hippurate will be performed by Kragerø Tablettproduksjon AS. The boxes will be labelled according to example (attachment) with corresponding labels for each country in local language.

5.1.3. Storage and handling

One pharmacy/medical distributor will be designated to be responsible for sending out the medication to the relevant sites in each country. The medication will be stored at each site in a locked cupboard in a secure access room. The sealed code envelopes will be kept together with the IMP in a locked cupboard. The monitor will check if any unauthorised code breaks has been performed during the study. IMPs will be stored according to storage instructions and local requirements with a controlled temperature not exceeding 30 degrees Celsius. Each study site will sign for sending out the IMP to the patient. Each study site will keep accountability logs and temp logs.

5.1.4. Drug accountability and treatment compliance

Any remaining non-used IMP will be gathered by a study nurse/phd-student by the end of 180 days of the trial and will be stored at the study site. The monitor will count remaining IMP and control treatment compliance and report this. Finally, the non-used IMP will be sent to the designated pharmacy for destruction. An accountability log will be made for each patient, including the batch number.

5.1.5. Destruction

Destruction of IMP will be performed at the designated pharmacy as stated above. Current medication taken by participants will be registered at inclusion. As interaction with other

medications are limited, there is no necessity to register changes in ongoing medication during the trial period with the exception of prescribed UTI antibiotics, sulphonamide antibiotics, alkalinizing substances (such as antacids), or in case of SAE report.

5.2. Blinding

Boxes are to be handed out sequentially to each participating patient following the number on the boxes, 4 identical boxes with 90 tablets in each box, in total 360 tablets. No information on the boxes reveals if the content is active drug or placebo. The electronic version of the Excel files (one for each country) will be available for the monitor in order to assist with emergency unblinding when needed. The staffs involved in these procedures are not to disclose this information to anyone else until all statistical analysis is done. One exception is if there is an SAE and it is deemed important to break the code.

Kragerø Tablettproduksjon AS will produce 400 identical sets of boxes labelled either “ImpresU study drug – number ZZZ” or “ImpresU study drug – number ZZZ” (ZZZ is a sequential number from 1-400). Patients, GPs meeting patients, pharmacists dispensing drugs, the investigators and persons involved in statistical analysis will not be aware of group allocation until all statistical analyses are done (triple blind).

5.3 Breaking the blinding in an emergency situation

The study code should only be broken for valid medical or safety reasons e.g. in the case of a severe adverse event where it is necessary for the treating physician to know which treatment the patient is receiving. There will be one sealed opaque envelope for each medication ID available, at the study sites, containing information of active substance or placebo regarding IMP. These envelopes will be stored together with the IMP. The treating physician contacts the coordinating centre or the PI via phone numbers available on patient/physician information cards regarding the study medication. On these cards, there will also be an emergency number provided by the Sponsor to be able to reach the code break envelope/list in emergency situations. The coordinating centre (or the Sponsor) provides the treating physician with the information as requested. On receipt of the treatment allocation details, the treating physician deals with the participant's medical emergency as appropriate. The PI documents the breaking of the code and the reasons for doing so on the CRF and in the site file. The PI notifies the Sponsor as soon as possible following the code break detailing the necessity of the code break.

5.4 Concomitant medication

Medications considered necessary for the patient's safety and well-being may be given at the discretion of the investigators unless not specified in the exclusion criteria. Concomitant medication will be recorded in the Case Report Form (CRF) at inclusion. As interaction with other medication is limited, there is no necessity to register changes in routine medication during the trial period with the exception of prescribed UTI antibiotics or in case of SAE report. In case of severe dehydration, or treatment with sulphonamide antibiotics the participant should temporarily pause IMP. Alkalizing substances (such as antacids) reduces the effect of methenamine hippurate and should be avoided.

Hence, patients requiring long term use of antacids will not be included, or withdrawn if there will be a need for long term use of alkalizing substances during the first six months when taking IMP.

6. STUDY MEASUREMENTS AND VARIABLES

- number of UTI antibiotic treatments (name of drug, dosage and duration) during day 2-360
- number of UTIs (acute symptoms specific/related to the urinary tract) during day 2-360
- registration of symptoms and severity when initiating treatment for UTI. This will be measured by a scale 0-6 (no symptoms to worst possible) for each of the three cardinal symptoms and general condition.
- registration of number of pyelonephritis and hospital admission for UTI
- laboratory tests at Visit 1: urine culture and dipstick urinalysis regarding pH, nitrite and leukocyte esterase
- laboratory tests ordered by the ordinary clinician in case of episodes of UTI during the study period (urinary dipsticks regarding nitrite and leukocyte esterase and urine culture)
- level of care: general practice, residential home care or nursing home
- SAEs, whereas relationship with IMP cannot be excluded.

6.1. Primary variable

(See section "2 Study Objectives and Endpoints").

6.2. Secondary variable(s)

(See section "2 Study Objectives and Endpoints").

6.3. Safety variable(s)

Pyelonephritis, hospitalization and death will be registered as safety endpoints. Methenamine hippurate has a well-documented safety profile and is a commonly used medication in primary care settings in Scandinavia. Therefore, non-serious adverse events (AE) will not be recorded in this study. All SAEs, whereas relationship with IMP cannot be excluded, occurring during the study period are recorded and reported according to guidelines in each country.

6.4. Biological sampling procedures

6.4.1. Handling, storage and destruction of biological samples

A urine specimen will be taken at the inclusion for culture and dipstick urinalysis regarding pH, nitrite and leukocyte esterase. The urine specimen will be destroyed after this.

In case of growth of pure cultures of *E. coli* in the inclusion urine culture, we will freeze the isolates of *E. coli* and send them to the department of clinical microbiology at Sahlgrenska University Hospital in Sweden for analysis of phylogenetic subgroups according to published protocols using PCR-technique.

Any episodes of acute UTI during the follow-up period (day 2-360) will be handled by regular health services (primary health care centres, OOH services or hospitals). The study team will order copies of medical records from acute UTI episodes including laboratory results regarding urinary dipsticks and urine culture. If feasible, we will also send pure culture *E. coli* isolates for phylogenetic typing as previously described.

6.4.2. Total volume of blood per patient

No blood tests will be taken in this study.

6.4.3. Biobank

The urine specimen taken at the inclusion visit for analysis of a urine dipstick and culture will not be registered in a biobank (if not required in national guidelines), as the urine specimen will be destroyed immediately after analysis. We will freeze isolates of *E.coli* from the inclusion urine culture, and if possible from some of the cultures taken during subsequent episodes of acute UTIs. Bacteria is not regarded human material and does not need a biobank registration.

7. SAFETY

7.1. Reference Safety Information

Anticipated adverse drug reactions in the study:

- Methenamine hippurate is well tolerated and adverse effects are generally mild (10)
- *According to SPC:*
- *Gastrointestinal disorders*
 - Uncommon: gastric irritation, irritation of the bladder, nausea, vomiting
 - Not known: diarrhoea, abdominal pain
- *Skin and subcutaneous disorders*
 - Uncommon: Rash, pruritus
- Alkalizing substances (such as antacids) reduces the effect of methenamine hippurate and should be avoided. Hence, patients requiring long term use of antacids will not be included or withdrawn if there will be a need for long term treatment with alkalizing substances when taking IMP during the first six months.
- Simultaneous intake of sulphonamide antibiotics can increase risk of crystalluria. Therefore, methenamine hippurate will temporarily be paused if the participant is prescribed a course of sulphonamide antibiotics.
- Except for those described above, there are no other known clinically relevant interactions between methenamine hippurate and other pharmaceuticals

7.2. Definitions

7.2.1. Adverse Event (AE)

An AE is any untoward medical occurrence in a patient or clinical investigation subject administered a medicinal product and which does not necessarily have a causal relationship with this treatment. An AE can therefore be any unfavourable and unintended sign (including an abnormal laboratory finding), symptom, or disease temporally associated with the use of a medicinal (investigational) product, whether or not related to the medicinal (investigational) product.

Causality

The investigator is responsible for determining whether there is a causal relationship between an AE and the use of a medicinal product.

AEs are categorized either as unrelated, possibly related or related, as defined below:

- **Unrelated:** the AE is not reasonable in relation to the use of the medicinal product, or another cause can itself explain the occurrence of the event.
- **Possibly related:** the AE may be explained by the medicinal product and the onset is reasonable in relation to the use of the medicinal product, however there is insufficient information to determine the likelihood of this possibility.
- **Related:** the AE is most likely explained by the medicinal product and the onset is reasonable in relation to the use of the medicinal product.

Severity

In addition to assessing the relationship of the administration of the investigational product(s) to adverse events, an assessment is required of the intensity (severity) of the event. The following over-all classifications should be used:

- **Mild:** An adverse event which is relatively mild and transient in nature, but can be an annoyance, and does not interfere with normal activities.
- **Moderate:** An adverse event which may be uncomfortable but is not hazardous to health. It may be sufficiently discomforting to interfere with normal activities but does not completely prevent them.
- **Severe:** An adverse event which is incapacitating and/or it is a hazard to the subject.

7.2.2. Adverse Drug Reaction (ADR)

Regarding marketed medicinal products: A response to a drug which is noxious and unintended and which occurs at doses normally used in man for prophylaxis, diagnosis, or therapy of diseases or for modification of physiological function.

7.2.3. Serious Adverse Event (SAE)

Any untoward medical occurrence that at any dose:

- results in death,
- is life-threatening,
- requires inpatient hospitalization or prolongation of existing hospitalization,
- results in persistent or significant disability/incapacity, or
- is a congenital anomaly/birth defect.

Medical and scientific judgement should be exercised in deciding whether an event is “serious” and if expected reported is appropriate in other situations, such as important medical events that may not be immediately life-threatening or result in death or hospitalization, but may jeopardize the subject or may require intervention to prevent one of the other outcomes listed in the definition above. These should also usually be considered SAEs.

7.2.4. Suspected unexpected serious adverse reaction (SUSAR)

A SUSAR is a serious adverse reaction of which nature or severity is not consistent with the applicable product information (e.g., Investigator's Brochure for an unapproved investigational product or package insert/summary of product characteristics for an approved product).

7.3. Reporting

7.3.1. Adverse Event (AE)

Methenamine hippurate has a well-documented safety profile and is a commonly used medication in primary care settings in Scandinavia. As a result of this no non-serious adverse events will be recorded in this study. All SAEs, whereas relationship with IMP cannot be excluded, occurring during the study period are recorded as detailed in Section 7.3.3 Reporting Procedures for Serious Adverse Events.

It will be left to the Investigator's clinical judgment to decide whether or not a symptom or side effect is of sufficient severity to require the participant's removal from treatment. A participant may also voluntarily withdraw from treatment due to what the participant perceives as an intolerable symptom or side effect.

7.3.2. Adverse Drug Reaction (ADR)

Methenamine hippurate has a well-documented safety profile and is a commonly used medication in primary care settings in Scandinavia. Therefore, non-serious AE will not be recorded in this study.

7.3.3. Serious Adverse Event (SAE)

All SAEs that is life threatening or results in death must be reported using the SAE Report Form by the person who has discovered the SAE or nominated delegate. The SAE form will be electronically submitted to the sponsor or delegate within 24 hours of the site study team becoming aware of the event.

SAEs requiring inpatient hospitalization or prolongation of existing hospitalization and AEs resulting in persistent or significant disability/incapacity will not be reported if being expected events in a frail elderly population (e.g. hip fracture, heart failure, ischemic heart disease). If these SAEs are related to UTI (e.g. pyelonephritis) they must be reported using the SAE Report Form by the person who has discovered the SAE or nominated delegate. If relationship with IMP cannot be excluded these SAEs are possibly, probably or definitely related to the trial medication. If so these adverse events must be reported as SAR (Serious Adverse drug Reaction) if expected and included in SmPC or as SUSAR (Suspected Unexpected Serious Adverse Reaction) if unexpected and not included in SmPC. SUSAR is further described in 7.3.4. The reason why only reporting these when relationship to IMP cannot be excluded: Methenamine hippurate is a well-known and widely used drug in Scandinavia with few and mild side effects which has been clinically used since many decades. There is no reason to expect any previously unknown AE and SAE to occur in this trial. Judgement whether related to UTI or the trial medication will be done by the PI of each country.

SAEs consisting of a congenital anomaly or birth defect is not relevant in this trial as all participants are women aged ≥ 70 years.

Please find safety reporting flow-chart in appendix 5.

SAEs will be registered throughout the studied period. In case of SAE present and not resolved by day 360, this SAE will be followed until resolution.

The sponsor or delegate will perform an initial check of the report, request any additional information, and ensure it is reviewed by the PI or other delegated personnel for relatedness and expectedness as soon as possible considering the reporting time for a potential SUSAR according to the relevant competent authority. Additional and further requested information (follow-up or corrections to the original case) will be detailed on a new SAE Report Form and submitted to the sponsor or delegate. See safety reporting flowchart in appendix 5. If the event has not resolved by day 360 the SAE will be reviewed again to see if resolution has occurred. If the event is considered “resolved” or “resolving” no further follow-up is required. If not, the event must be followed up until such a time point.

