2. STUDY OBJECTIVES AND ENDPOINTS

The primary objective of this study is to investigate if taking methenamine hippurate reduce the need for antibiotic usage due to recurrent UTI (measured as number of antibiotic courses). The remaining objectives are considered secondary. Pyelonephritis, hospitalization and death will be registered as safety endpoints in the study.

Objectives	Outcome Measures / variables / endpoints	Time point(s) of evaluation of this outcome measure (if applicable)
Primary Objective		
1 The primary objective of this study is to investigate if taking methenamine hippurate reduces the need for antibiotic usage due to recurrent UTI (measured as number of antibiotic courses).	Number of UTI antibiotic treatments during the six months of treatment. If the participant receives >1 antibiotic course for UTI without symptom relief it is regarded as one episode and counted as one antibiotic treatment. If there has been an asymptomatic period of at least 14 days in-between two UTI antibiotic	After six months of treatment.

		courses, this is regarded as a new antibiotic treatment.	
Secondary Objectives			
2a	To investigate if methenamine hippurate will have a prolonged effect on antibiotic usage even after discontinuation.	Number of UTI antibiotic treatments during the six months following completion of treatment. If the participant receives >1 antibiotic course for UTI without symptom relief it is regarded as one episode and counted as one antibiotic treatment. If there has been an asymptomatic period of at least 14 days in-between two UTI antibiotic courses, this is regarded as a new antibiotic treatment.	Six months after completing (12 months after commencing) treatment.
2b	To investigate if taking methenamine hippurate reduces the incidence of UTI.	Number of UTIs (acute symptoms specific/related to the urinary tract) during the six months of treatment. If the participant has had >1 UTI episode without symptom relief it is regarded as one episode. If there has been an asymptomatic period of at least 14 days in-between two UTI episodes, this is regarded as a new episode.	After six months of treatment.
2c	To investigate if methenamine hippurate can reduce severity of UTI symptoms.	Registration of symptom severity when initiating treatment for UTI.	After six months of treatment.

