9. DATA MANAGEMENT

9.1. Recording of data

The investigator will ensure that all data collected in the study are recorded in a timely manner according to any instructions provided. An electronic Case Report Form (eCRF) will be used for data collection. The investigator will ensure that the data are recorded and that any corrections in the CRF as specified in the study protocol and in accordance with the instructions provided. The investigator ensures the accuracy, completeness and timeliness of the data recorded.

Research Online (RO) is an electronic data capture (EDC) system that will be used for data collection. Web-based case report forms (eCRF) are implemented into the system to facilitate the study specific data collection. These forms can easily be accessed by all standard web browsers. The baseline CRF at inclusion, telephone follow-up in case of acute UTI episode(s), telephone contact by end of treatment, telephone contact by end of study and SAE Forms will be entered onto this system. Some sites may choose to first register data in a paper version of the CRF that will later be entered into the eCRF by the coordinating centre. The investigator will sign the completed CRF. A copy of a completed paper CRF will be archived at the study site. The original paper CRF will be archived at the coordinating centre in each country.

Multiple validation and range checks will be programmed in the eCRF to assure complete and high-quality data. Data that does not comply with these rules or ranges will generate a query that must be resolved immediately or at a later stage. Electronic workflows will employ multiple skip and jump rules to ensure that only information that is applicable to the patient will appear. After the data of the last subject is entered, the clean file will be produced and thereafter the database will be closed and data made available for further analysis and publication purposes.

RO meets all requirements according to GCP standards for electronic data entry with respect to safeguarding data integrity and data security regulations. Users will have role-based access to the system by logging in using their personal username and password. The system will log all data entry steps with timestamps and user information. The role-based access to the system will avoid unauthorised data access and prevents users from performing actions that they do not have authorisation for.

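### Hospitalization is named without restriction as a safety endpoint, but non-UTI admissions judged unrelated to study drug have no described route into the data

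*Protocol*

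**What the plan says.** **The endpoint.** Protocol section 2 states: "Pyelonephritis, hospitalization and death will be registered as safety endpoints in the study". Protocol 6.3 says the same, and SAP sections 2 and 4.3 repeat it. No cause of admission is attached.

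**The recording rule.** Directly after naming the endpoint, Protocol 6.3 limits what is kept: "All SAEs, whereas relationship with IMP cannot be excluded, occurring during the study period are recorded and reported". Protocol 7.3.1 repeats the limit: "All SAEs, whereas relationship with IMP cannot be excluded, occurring during the study period are recorded as detailed in Section 7.3.3". The call content in Protocol 3.4 and the variable lists in Protocol section 6 and SAP section 4 apply the same condition. The only admission variable in those lists is admission for UTI.

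**The reporting rule.** Protocol 7.2.3 counts as serious any event that "requires inpatient hospitalization or prolongation of existing hospitalization". Protocol 7.3.3 then says that such events, and disabling ones, "will not be reported if being expected events in a frail elderly population (e.g. hip fracture, heart failure, ischemic heart disease"). UTI-related events must still be reported, as must those whose relation to study drug cannot be excluded. Fatal and life-threatening SAEs must all be reported, with no condition on relatedness or expectedness. The principal investigator of each country decides relatedness to UTI or study drug.

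**Looser text.** Protocol 7.3.3 also says, without a filter, that SAEs are registered throughout the study period. The SAE row in the visit table (Protocol 3.3, SAP 3.2) carries no filter either.

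**The concern.** The endpoint sentence promises a count of hospitalizations. The collection rules describe a smaller set, selected by two judgements: whether the event is related to study drug or UTI, and whether it is expected in frail elderly people. The second has three examples and no definition.

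The stated reason for the trial is partly to clarify the safety of longer-term use (Protocol 1.1). Non-serious adverse events are not recorded (Protocol 6.3), so serious events carry nearly all of the safety evidence. A harm that resembles ordinary illness in women over 70 would be hard to recognise case by case. It could appear only as a difference in counts between randomised arms, and that comparison needs counts taken before any causality judgement.

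**Working it through.** The plan states no figure on this point, so there is none to reproduce. The check follows each kind of admission through the rules.

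| Event | Route in the documents | Result |
|---|---|---|
| Admission for UTI | Call and medical record (3.4), variable list (6), SAE form (7.3.3), objective 2e | Captured and analysed |
| Non-UTI admission, relation to study drug not excluded | 6.3, 7.3.1, 7.3.3 | Captured |
| Non-UTI admission, judged unrelated, expected type | Not reported under 7.3.3; outside the recording rule in 6.3 and 7.3.1 | No described route |
| Non-UTI admission, judged unrelated, not an expected type | 7.3.3 exempts only expected events, but its rationale and 6.3 and 7.3.1 leave unrelated ones out | Unclear; no route under 6.3 |
| Fatal or life-threatening event | Reportable without a filter (7.3.3); 6.3 and 7.3.1 do not repeat this | Covered, wording to align |

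**Is this only a reporting rule?** The 7.3.3 sentence by itself is. The recording gap rests on 6.3, 7.3.1, 3.4 and the variable lists, which restrict what is recorded.

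**Other routes.**
- Protocol 9.1 lists the baseline form, the acute-UTI follow-up, and "telephone contact by end of treatment, telephone contact by end of study and SAE Forms will be entered onto this system". No all-cause admission form is named.
- The end-of-study GP record review in 3.4 is there to validate the number of UTI episodes.

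**Judgement.** Protocol 7.2.1 defines three causality classes: unrelated, possibly related and related. Sections 4.4.2 and 7.3.3 use possibly, probably and definitely. The filter therefore rests on a scale that the protocol does not define consistently, applied by four country investigators. The text describes no central adjudication.

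**Analysis.** SAP 5.1 covers admissions only through objective 2e. It gives no by-arm analysis of all-cause hospitalization or of deaths.

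**Illustration on assumptions.** The documents give no admission rate and no capture fraction. Assume 200 women per arm, two-sided alpha 0.05, a true risk ratio of 1.5 for having at least one admission in 12 months, control risk *p*, and the same captured fraction *c* in both arms. Then p1 = c·p, p2 = 1.5·c·p, p̄ = (p1 + p2)/2, and

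power = Φ{[(p2 − p1) − 1.96·√(p̄(1 − p̄)·2/200)] / √[p1(1 − p1)/200 + p2(1 − p2)/200]}.

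For p = 0.20 and c = 1: (0.10 − 1.96 × 0.0433)/0.0430 = 0.352, so power is 64%. For c = 0.5: (0.05 − 1.96 × 0.0331)/0.0330 = −0.449, so power is 33%.

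| Control risk | Full capture | Half | Quarter |
|---|---|---|---|
| 10% | 33% | 18% | 11% |
| 20% | 64% | 33% | 18% |
| 30% | 88% | 48% | 25% |

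A uniform *c* is lenient, because the documented filter acts on the type of admission. If an excess fell mainly in diagnoses regarded as expected and unrelated, it would be removed from the comparison rather than diluted.

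**The case against.** **Hospitalization may mean admission for UTI.** It stands next to pyelonephritis in the sentence, and objective 2e pairs pyelonephritis with UTI admission. On that meaning the endpoint is collected and analysed, and the defect is two missing words. This is a fair alternative and the text does not settle it. Against it, objective 2e and the variable lists say UTI when they mean it, whereas the safety sentence does not and also includes death.

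**An unseen form may fill the gap.** The list in 9.1 gives form names rather than fields, and it omits the 30-day calls that 3.3 and 3.4 require, so it is not exhaustive. The form content and the appendix 5 flow-chart were not available. The unfiltered SAE rows and the unqualified sentence in 7.3.3 also point towards wider registration. This stands. A reader might infer that all-cause admissions cannot be counted, but the documents show only that no route is described and that the passages conflict.

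**Deaths are covered.** A reader might extend the gap to deaths. Section 7.3.3 requires every fatal or life-threatening SAE to be reported, so that extension fails. Only the missing by-arm table and the wording of 6.3 and 7.3.1 remain.

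**Selective SAE reporting is a reasoned choice for a long-marketed drug.** Agreed. Reporting and endpoint capture are separate matters, and the reporting rule can stay.

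**The comparison would be weak anyway.** At assumed control risks of 10% and 20%, even full capture gives only 33% and 64% power. That argues for an estimate with an interval rather than a test. It does not argue for an incomplete count.

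**Conclusion.** The point holds as an inconsistency between a named endpoint and the collection described for it. Followed as written, 6.3, 7.3.1 and 7.3.3 leave out non-UTI admissions judged unrelated. The remaining count would be incomplete and would depend on investigators' judgement. UTI admissions, possibly related SAEs, deaths and life-threatening events are not part of the gap, and the primary analysis is unaffected.

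The size is unknown. The power figures rest wholly on assumed risks, an assumed risk ratio and assumed capture fractions. Two further inferences lack support. One is that most admissions would be lost: nothing in the documents gives the share that is expected or unrelated. The other is that capture would differ between arms. Blinding makes that unlikely, although it does not restore the lost events.

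**What to change.** 1. **Keep the SAE reporting rule in 7.3.3 and separate endpoint capture from it.** Record every hospital admission, with date and main reason, at the existing 30-day, day 180 and day 360 calls.
2. **Add to the SAP** a table of all-cause admissions and deaths by randomised arm, with an estimate and confidence interval and no causality filter.
3. **Reconcile the text.** Align the SAE rows in Protocol 3.3 and SAP 3.2 and the unqualified sentence in 7.3.3 with 6.3 and 7.3.1. Repeat in 6.3 and 7.3.1 that fatal and life-threatening SAEs are recorded whatever the cause.
4. **Optional:** extend the end-of-study GP record review from UTI episodes to admissions. No routine call is scheduled between day 180 and day 360, so this would support recall over those six months.

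The cost is one question on calls already planned, one table and a few wording changes. The wider GP review would add a small workload.

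**Alternative:** if only UTI admissions are meant, restrict the endpoint to them in Protocol sections 2 and 6.3 and SAP sections 2 and 4.3, and draw no all-cause safety conclusion from the trial.
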